6.0 TRIAL PROCEDURES*

Figure 2-

[figure not shown]

Table 1-

Trial Period:	Screening Phase	On-Treatment Monitoring Visit							Post-Treatment
		Week 1	Week 2	Week 3	Week 4	Week 5	Week 6		
	Study Screening								Survival Follow-Up
Scheduling Window (Days):	4 weeks to 0 days prior to beginning of CRT	Fraction 1-5 of CRT	Fraction 6-10 of CRT	Fraction 11-15 of CRT	Fraction 16-20 of CRT	Fraction 20-25 of CRT	Fraction 26-29 of CRT if applicable		12+/-4 wks after end of CRT and then per SOC FU algorithm (Table 2)
Administrative Procedures									
Informed Consent	X								
Medical History	X								
Survival Status									X ^c
Clinical Procedures/Assessments									
Directed Physical Examination	X ^a	X	X	X	X	X	X		X
Weight	X	X	X	X	X	X	X		X
ECOG Performance Status	X	X	X	X	X	X	X		X
Radiation CT-Simulation	X ^b	X ^b	X ^b	X ^b	X ^b	X ^b	X ^b		
Physician-assessed CTCAE v4		X	X	X	X	X	X		X ^c
Patient-reported PRO-CTCAE		X	X	X	X	X	X		X
Chemoradiation Treatment		X	X	X	X	X	X		
Laboratory/Imaging/Assessments									
Pregnancy Test – Urine or Serum HCG	X								
CBC with Differential including ANC and ALC	X	X	X	X	X	X	X		X
Quality of Life Questionnaires	X ^d								X ^d
PET/CT + contrast or CT chest/abdomen/pelvis with contrast	X								X
Anoscopy or Flexible Sigmoidoscopy	X								X ^e

Trial Period:	Screening Phase	On-Treatment Monitoring Visit						Post-Treatment
		Week 1	Week 2	Week 3	Week 4	Week 5	Week 6	
Scheduling Window (Days):	Study Screening 4 weeks to 0 days prior to beginning of CRT	Fraction 1-5 of CRT	Fraction 6-10 of CRT	Fraction 11-15 of CRT	Fraction 16-20 of CRT	Fraction 20-25 of CRT	Fraction 26-29 of CRT if applicable	Survival Follow-Up 12+/-4 wks after end of CRT and then per SOC FU algorithm (Table 2)

*All are standard-of-care tests/procedures/charges.

- a. The first physical examination during the screening period will be a full examination, all subsequent examinations will be directed
- b. Patients will be simulated followed approximately one week or more prior to starting radiation therapy. Initial CT simulation is required for treatment planning, and at least one verification CT simulation is required during treatment, but verification CT simulations can be done as often as weekly at the discretion of the treating physician.

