- c. In lieu of an in person visit, all subsequent follow ups after the first follow up can be conducted over the phone. In these instances a directed physical examination will not be required and appropriate outside imaging scans must be utilized to assess response.
- d. EQ-5D, EORTC QLQ -C30, Perceived Stress Scale, FSFI (women) and IIEF (men).
- e. Baseline and 12 week follow up endoscopy must be performed at MD Anderson. Schedule of follow up endoscopies after the 12 week follow up will be decided by the managing team based on findings.

Figure 2 and Table 1 above summarize the trial procedures to be performed at each visit. Individual trial procedures are described in detail below. Patients are strongly encouraged to maintain follow up at MD Anderson. If unable to do so due to unexpected logistical or financial consideration, patients will be advised to maintain the follow up schedule with an outside oncologist as per the current standard of care- and have all imaging and clinical documentation forwarded to MD Anderson. Additional history and/or QOL instruments will be emailed via REDCap or collected over the phone as needed by the study team. The first follow up study visit as well as all required tests at 12+/-4 weeks after completion of CRT will be required to be at MD Anderson.

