6.1.10 Patients will report baseline symptoms and quality of life with the following instruments as outlined below. Questionnaires will be administered electronically and paper copies of the questionnaires will be available if necessary.

- The EQ-5D-5L
- The EORTC QLQ-C30 will be utilized to report GI-specific quality of life
- The Perceived Stress Scale
- For female patients:
Female Sexual Function Index (FSFI)- 19 question survey validated in cancer survivors.
- For male patients:
Individual Items of International Index of Erectile Function Questionnaire (IIEF).

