7.4 Statistical Analysis Plan

7.4.1 Primary Clinical Endpoint: *To assess physician-reported acute grade 3 or greater gastrointestinal, genitourinary and hematologic toxicities at 12 weeks post-treatment for patients treated with linear energy transfer (LET)-optimized, intensity-modulated proton therapy (IMPT) and compare to contemporary controls treated with VMAT to determine the feasibility of this outcome for a future randomized trial.*

- At baseline, weekly during treatment, and at the 12 week post-treatment follow up appointment, the treating physician will document physician-assessed acute hematologic, gastrointestinal, genitourinary, dermatologic and other toxicities according to the Common Toxicity Criteria for Adverse Events v-4 (CTCAE v4).
- For each cumulative physician-reported toxicity (hematologic, gastrointestinal, genitourinary, dermatologic and other) at 12-weeks post-treatment, we will tabulate results by type, grade, and attribution and compare with contemporary controls treated with standard of care VMAT-based chemoradiation with 5FU and cisplatin for non-metastatic anal squamous cell carcinoma manually and individually matched for (in order): T-stage, radiation dose, age and gender. We will compare toxicity rates using a McNemar's chi-squared test for paired proportions.
- A separate PA protocol will be submitted to retrospectively review the data from these contemporary controls.
- Subset analyses will be carried out to evaluate the effect of other variables that may also impact toxicity in addition to radiation modality (IMPT vs VMAT).

On RTOG 0529, patients treated with dose-painted IMRT-based concurrent CRT for anal cancer had reported worst overall G3 or greater toxicity rates of 83%. GU/GI G3 or greater toxicity rates were 21%, dermatologic G3 or greater toxicity rates were 23% and hematologic G3 or greater toxicity rates were 58% ⁴.

To ensure an LET-optimized IMPT-based CRT approach is not overly toxic, we will monitor physician-assessed toxicity using the Bayesian optimal phase 2 (BOP2) design ²⁸. Specifically, let n denote the interim sample size and N denote the maximum sample size. Let p_{tox} denote the probability of G4 or greater toxicity and define the null hypothesis $H_0: p_{tox} > 0.5$, representing that the treatment is too toxic. We will stop enrolling patients and inspect the safety data for possible trial termination if

$$Pr(p_{tox} \leq 0.5 | data) < \lambda \left(\frac{n}{N}\right)^\alpha,$$

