- Secondary Endpoint #4: *To evaluate local progression-free survival, distant metastasis-free survival and overall survival at 24 and 48 months.*
 - Patients will follow up with their treating physician at every 3-6 months per the current standard of care MD Anderson gastrointestinal center follow-up algorithm (Table 2).
 - Local Failure/Progression: Either recurrence of disease in the anal canal following clearance, progression of disease in the anal canal after completion of treatment or persistence of disease in the anal canal for more than 6 months after completion of treatment.
 - Distant Metastatic Failure: the appearance of distant metastatic disease.
 - Disease-Free Survival: measured as time to locoregional failure, appearance of distant metastases or death due to any cause.
 - Overall Survival: measured as time due to death due to any cause.
 - We will estimate LPFS, DMFS, and OS from time of enrollment using the Kaplan-Meier method and report estimates with appropriate 95% confidence intervals.
 - For local and regional failure, the date of failure will be recorded as 6 months after the completion of treatment in the case of persistent, biopsy-proven disease after 6 months status-post completion of all therapy.
- Secondary Endpoint #5: *To evaluate rates of patient-reported acute toxicity, function, distress and QOL at 12 weeks post-treatment.*

- PRO-CTCAE will be collected weekly during treatment and also at the 12 week post-treatment follow up visit
- EQ-5D will be collected at baseline and also at the 12 week post-treatment follow-up visit
- The EORTC QLQ- C30will be collected at baseline and also at the 12 week post-treatment followup visit
- Treatment-Related Stress Questionnaire and the Perceived Stress Scale will be collected at baseline and also at the 12 week post-treatment followup visit
- For female patients:
 - Female Sexual Function Index (FSFI)- 19 question survey validated in cancer survivors will be collected at baseline and also at the 12 week post-treatment followup visit.
- For male patients:
 - International Index of Erectile Function Questionnaire (IIEF) will be collected at baseline and also at the 12 week post-treatment followup visit

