- For patient-reported acute toxicity, function, distress and QOL instruments, we will graph and summarize the distributions of scores for each instrument over time noting how many patients have data at each time point. We will analyze the changes over time using mixed effects linear models.

- Secondary Endpoint #6: *To evaluate rates of patient-reported late toxicity, function, distress and QOL every 6 months for 24 months.*
 - PRO-CTCAE, EQ-5D, EORTC QLQ-C30, treatment-related stress questionnaire, perceived stress scale, female sexual function index, and international index of erectile function questionnaire will be collected every 6 months following treatment until 24 months post-treatment.
 - For patient-reported acute toxicity, function, distress and QOL instruments, we will graph and summarize the distributions of scores for each instrument over time noting how many patients have data at each time point. We will analyze the changes over time using mixed effects linear models.

- Secondary Endpoint #7: *To evaluate the value of proton therapy by comparing Time-Driven Activity-Based Costing data from the date of consultation until the date of the 12-week follow up visit post-treatment with contemporary controls treated with VMAT.*
 - TDABC data will be collected for the entire acute episode of care from the date of consultation until the 12-week follow up post-treatment for all patients using previously generated departmental process maps. Costs will be tabulated as either treatment or toxicity-management related.

We will then compare these TDABC data with contemporary controls treated with VMAT (as described above) treated during the same fiscal year.

7.4.3 Exploratory Endpoints:

- Exploratory Endpoint #1: *To compare dose to the pelvic bone marrow, bowel, bladder and genitalia between LET-optimized IMPT, traditionally optimized IMPT and VMAT.*
 - Dosimetric studies will be performed comparing the doses from plans generated using the techniques described above.

- We will record dosimetric differences between conventionally optimized (RBE = 1.1) IMPT plans and LET-optimized IMPT plans for analysis using the Wilcoxon rank-sum test. We will also record how often the LET-optimized IMPT plan is chosen by the treating physician over the conventionally optimized (RBE = 1.1) IMPT plan.

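### Baseline physician CTCAE is required by the analysis plan but not scheduled, PRO-CTCAE has no pre-treatment assessment, and the Treatment-Related Stress Questionnaire is analysed but never scheduled

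*Combined protocol and SAP*

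**What the plan says.** **Physician CTCAE.** Section 7.4.1 asks for grading "At baseline, weekly during treatment, and at the 12 week post-treatment follow up appointment". It then tabulates cumulative toxicity by type, grade and attribution, and compares rates with matched VMAT controls by McNemar's test. In Table 1 the row "Physician-assessed CTCAE v4" is empty under screening and marked for weeks 1 to 6 and post-treatment.

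**PRO-CTCAE.** The Table 1 row "Patient-reported PRO-CTCAE" has the same pattern. Secondary Endpoint #5 states that "PRO-CTCAE will be collected weekly during treatment and also at the 12 week post-treatment follow up visit". Section 6.1.10 opens with "Patients will report baseline symptoms and quality of life with the following instruments as outlined below", but PRO-CTCAE is not in the list that follows. For the patient-reported instruments the plan says "We will analyze the changes over time using mixed effects linear models".

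**Treatment-Related Stress Questionnaire.** Secondary Endpoint #5 says the "Treatment-Related Stress Questionnaire and the Perceived Stress Scale will be collected at baseline" and again at 12 weeks. Secondary Endpoint #6 adds every 6 months to 24 months. Table 1 footnote d names five instruments ("EQ-5D, EORTC QLQ -C30, Perceived Stress Scale, FSFI (women) and IIEF (men"), and this questionnaire is not among them.

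**The concern.** Site staff normally work from the schedule of procedures. If they follow Table 1 and section 6, three things are lost: the pre-treatment physician grade that section 7.4.1 calls for, any pre-treatment PRO-CTCAE value, and all data on one of the two stress instruments.

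Week 1 does not replace a baseline, because Table 1 defines it as fractions 1 to 5 of chemoradiation. The GI and GU items graded under section 6.2.3 include anal pain, proctitis, constipation, fecal incontinence and perineal pain, which an anal tumor can itself produce. Without a graded starting point, a grade 3 symptom present at diagnosis and recorded in week 1 cannot be separated cleanly from one caused by treatment. The primary endpoint is cumulative, so such a symptom can count.

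**Working it through.** The plan states no figure on this point, so the main check is a comparison of the sections.

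| Assessment | Section 7.4 | Table 1, screening | Section 6.1 | Section 6.2 / 6.3 |
|---|---|---|---|---|
| Physician CTCAE | Baseline, weekly, 12 weeks | Empty | Not listed | Starts at weekly on-treatment visits (6.2.3) |
| PRO-CTCAE | Weekly, 12 weeks, then 6-monthly; no baseline | Empty | Not in 6.1.10 | Weekly (6.2.3), 12 weeks (6.3.7), 6-monthly (6.3.8) |
| Treatment-Related Stress Questionnaire | Baseline, 12 weeks, 6-monthly | Not in footnote d | Not in 6.1.10 | Not in 6.3.7, hence not in 6.3.8 |
| EQ-5D, QLQ-C30, Perceived Stress Scale, FSFI, IIEF | Baseline, 12 weeks, 6-monthly | Footnote d | In 6.1.10 | In 6.3.7 and 6.3.8 |
| CBC with differential | Nadirs analysed | Marked | In 6.1.9 | Weekly and first follow-up |

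Rows 1 and 3 are contradictions between the analysis plan and the procedures. Row 2 is a gap that both share. The running text of section 6 repeats what Table 1 shows, so the empty cells are not a table-reading artefact.

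**Does anything else supply the missing baseline?**
- Section 6.4.2 assesses new or worsening adverse events and records causality, but on the timing of the trial flow chart, which has no baseline grade.
- Section 6.1.1 records active conditions without CTCAE grades and keeps details of the study disease apart from medical history.
- Section 7.4.1 tabulates attribution. It does not say whether only attributable or worsened events enter the rate that is compared.
- Section 7.3 makes a patient evaluable for toxicity with one weekly assessment, so a missing baseline would not be flagged.

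**Illustration of size.** Let *b* be the share of patients with a pre-existing grade 3 or greater GI/GU symptom that is counted as toxicity. The documents give no value, so *b* is an assumption, shown from 5% to 20%. Take 21% as the treatment-caused rate (the GU/GI figure that section 7.4.1 cites), assume a halving to 10.5% with IMPT, and assume that pre-existing and treatment-caused events are independent. The observed rate is 1 − (1 − p)(1 − b).
- Inflation of a 21% rate: (1 − 0.21) × b = 0.79b.
- Observed difference if both groups are affected alike: 10.5 points × (1 − b).

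| b | Patients of 40 | 21% reads as | 10.5% reads as | Difference (true 10.5 points) |
|---|---|---|---|---|
| 5% | 2 | 24.95% | 14.98% | 9.98 |
| 10% | 4 | 28.90% | 19.45% | 9.45 |
| 15% | 6 | 32.85% | 23.93% | 8.93 |
| 20% | 8 | 36.80% | 28.40% | 8.40 |

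The absolute rate moves by 4.0 to 15.8 points. The between-group difference moves by only 0.5 to 2.1 points, provided both groups are counted in the same way. If pre-existing symptoms were removed from one group only, the shift of about 0.79b would fall entirely on the comparison. With no true difference at 21%, and b = 10%, that alone would produce 0.79 × 10 = 7.9 points in favour of the adjusted group.

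**The case against.** The strongest defence has four parts.

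1. **No rule counts tumor symptoms as toxicity.** Attribution, causality and new-or-worsening language are all in the protocol. This stands: a reader might infer that presenting symptoms will be scored as toxicity, but the documents show only that they can be, because nothing says how attribution or worsening enters the McNemar rate.
2. **The primary endpoint does have some baseline data.** Baseline CBC with differential is required, eligibility sets floors for ANC, platelets, hemoglobin and WBC, and the hematologic component has the highest cited component rate (58%). This stands and confines the concern to graded GI and GU symptoms. Nor is it certain that no baseline grade will be recorded, since section 7.4.1 does ask for one.
3. **For PRO-CTCAE the schedule and the analysis plan agree.** Neither asks for a baseline, and a rate at 12 weeks needs none. This stands, so it is a design gap and not an inconsistency. A reader might infer that change cannot be estimated at all. That is too broad: PRO-CTCAE change from week 1 can be modelled, and the five instruments in 6.1.10 have baselines.
4. **A worse-than-baseline event rule could do harm.** Controls come from retrospective review under a separate protocol, and the documents do not show that they have baseline grades. Applied to IMPT patients alone, the rule would favour IMPT. This stands and shapes the remedy.

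The defence does not explain the missing screening mark or the unscheduled questionnaire, and none of the existing safeguards provides a graded GI/GU starting point.

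**Conclusion.** The point holds in this form. Two items are contradictions to reconcile: baseline physician CTCAE, and the Treatment-Related Stress Questionnaire. One is a design gap: with no pre-treatment PRO-CTCAE, change from before treatment cannot be estimated for any patient. The consequence for the primary endpoint is a possibility limited to GI and GU symptoms, and its size cannot be determined from the documents. The table above rests on an assumed *b*, on independence, on the cited 21% and on an assumed halving. Under those assumptions the descriptive toxicity rate is more exposed than the matched difference, unless the two groups are counted differently. Matching on T-stage, radiation dose, age and gender does not guarantee equal baseline symptoms.

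A reader might extend this to the safety stopping rule. That rule counts grade 4 or greater toxicity, and the documents give no ground for supposing that presenting symptoms at that grade would affect it.

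This is a cheap improvement, worth making because a patient-reported baseline that is missed cannot be recovered later.

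**What to change.** - Add screening marks in Table 1 for physician CTCAE and for PRO-CTCAE. Add both to section 6.1, with PRO-CTCAE in the 6.1.10 list and in the Secondary Endpoint #5 timing.
- Use baseline PRO-CTCAE as the first time point in the mixed model.
- State in section 7.4.1 how attribution and pre-existing grades enter the toxicity rate. Keep the primary McNemar comparison on one event definition that can be applied identically to IMPT patients and the retrospective VMAT controls.
- Use a definition of grade 3 or greater and worse than baseline in that comparison only if baseline grades can be abstracted for controls. Otherwise report it descriptively for IMPT patients.
- Either schedule the Treatment-Related Stress Questionnaire in footnote d, 6.1.10 and 6.3.7 (section 6.3.8 then follows), or delete it from Secondary Endpoints #5 and #6.

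The cost is one grading and one questionnaire, a few minutes of physician and patient time at a screening visit that already takes place. Keeping the stress questionnaire adds one more form at each time point. Using the adjusted definition in the comparison adds chart abstraction of baseline symptoms for controls.

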3.1 Background

The current standard of care for squamous cell carcinoma of the anal canal was established by RTOG 9811 and includes definitive CRT with 5-fluorouracil (5FU) and mitomycin-C (MMC)¹. However, studies have shown equivalent results with 5FU with cisplatin as concurrent treatment², so that regimen is also used at some centers, including MDACC³. Intensity modulated radiotherapy (IMRT) emerged as the new standard of care in the treatment of anal cancer when RTOG 0529, a phase II study, prospectively showed that IMRT was able to significantly reduce G2+ hematologic and G3+ dermatologic toxicity⁴.

The landmark studies establishing CRT as the standard of care utilized 3D treatment techniques. As such, large volumes of bowel, bladder, external genitalia and skin received significant doses. On the MMC arm of RTOG 9811, G3-4 hematologic and non-hematologic acute toxicity rates were 61% and 74%, respectively¹. Although IMRT was shown to reduce toxicity, patients receiving IMRT with concurrent 5FU and MMC on RTOG 0529 still experienced 77% G2+ gastrointestinal, 73% G2+ hematologic and 23% G3+ dermatologic toxicity. Additionally, bone marrow dose is typically higher with IMRT⁵, and the importance of bone marrow dose in predicting the risk of hematologic toxicity for patients receiving CRT for anal cancer has been established. Specifically, the volume of pelvic bone marrow receiving 5, 10, 15 and 20 Gy were all significantly associated with decreased WBC and ANC nadirs⁶.

The advantages of proton therapy (PT) arise from the physical properties of proton beams⁷. From a physical standpoint, proton beam dose deposition is highly favorable, following a Bragg curve as a function of its depth in tissue. The lower entrance doses and elimination of exit doses can produce superior conformal dose distributions to the target volume compared with radiotherapy with megavoltage (MV) x-rays. Thus, the rationale for using protons lies in reducing the integral dose and sparing surrounding healthy tissues and critical organs, minimizing treatment related complications and reducing the risk of radiation-induced secondary cancers^{8,9}.

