4.0 INCLUSION AND EXCLUSION CRITERIA

4.1 Inclusion criteria

- 1.) Histologically-proven, non-metastatic invasive primary squamous cell carcinoma of the anal canal (Stages I, II, and III).
- 2.) History/physical examination within 60 days prior to registration.
- 3.) Anal examination with biopsy on either colonoscopy, sigmoidoscopy, rigid proctoscopy or anoscopy.
- 4.) CT scan of the chest and abdomen with contrast or contrast-enhanced PET/CT scan within 60 days of registration unless the patient has a documented contrast allergy.

- 5.) CT scan of pelvis with contrast or contrast-enhanced PET/CT scan within 60 days of registration unless the patient has a documented contrast allergy.
- 6.) Zubrod Performance Status of 0-1 within 60 days prior to registration.
- 7.) Age \geq 18 years – 85 years.
- 8.) Laboratory data within 30 days prior to study registration showing:
 - Absolute neutrophil count (ANC) \geq 1.8 K/ μ L
 - Cannot be achieved through GCSF use
 - Platelets \geq 100 K/ μ L
 - Cannot be achieved through transfusion.
 - Hemoglobin \geq 8g/dL
 - Cannot be achieved through transfusion.
 - Serum creatinine \leq 1.5mg/dL
 - Bilirubin \leq 1.4mg/dL
 - Except in the case of patients with Gilberts disease.
 - White blood cells (WBC) \geq 3000/microliter
 - AST/ALT < 3x the upper limit of normal
- 9.) HIV test must be done within 90 days of study registration. If HIV positive, CD4 count must be obtained within 90 days of study registration. Note: HIV positive patients are eligible for this study if they have a CD4 count >400 cells/mm3.
- 10.) The patient must either have insurance authorization or otherwise secure funding to cover IMPT.
- 11.) The patient must be able to receive concurrent chemotherapy.

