4.2 Exclusion criteria

- 1.) Prior invasive malignancy (except non-melanomatous skin cancer), unless disease free for a minimum of 3 years.
- 2.) Prior systemic chemotherapy for anal cancer.
- 3.) Prior radiotherapy to the pelvis that would result in overlap of radiation fields.
- 4.) Evidence of distant metastatic disease (M1).
- 5.) Not receiving concurrent chemotherapy
- 6.) Women of childbearing potential or men who do not agree to use a medically effective form of birth control throughout their participation in the treatment phase of the study.
- 7.) Severe, active co-morbidity defined as follows:
 - unstable angina and/or congestive heart failure requiring hospitalization within the last 6 months.
 - transmural myocardial infarction within the last 6 months.
 - acute bacterial or fungal infection requiring intravenous antibiotics at the time of registration.
 - Chronic Obstructive Pulmonary Disease exacerbation or other respiratory illness requiring hospitalization or precluding study therapy at the time of registration.
 - hepatic insufficiency resulting in clinical jaundice and/or coagulation defects.
 - HIV positive with a CD4 count <400 cells/mm3.
 - other immunocompromised status.
 - women who are pregnant or lactating.
 - uncontrolled infection as deemed by the PI.
 - patient incarceration.

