6.5 Correlative Analyses

6.5.1 Both traditionally-optimized IMPT and LET-optimized IMPT plans will be generated for each patient enrolled on study. The goal of LET-optimized IMPT is to maximize the LET within the target and minimize it in normal tissues while maintaining the coverage requirements for target volumes and dose volume constraints for OARs expressed in terms of (RBE=1.1) weighted doses. This requirement is imposed to assure safety and for consistency with the current practice. The difference in dose distribution between IMPT and LET-optimized IMPT plans is expected to be minimal to moderate. Even though constraints are fully met, due to possible redistribution of high LET values from normal tissues into target volumes in LET-optimized IMPT plans, for some cases mean dose to surrounding critical organs may be increased. Our goal is to evaluate the safety of such differences in dose distributions.

6.5.2 Blood will be drawn at baseline, weekly during chemoradiation and at the 12-week post-treatment follow up visit as per standard of care (Table 1). WBC, ANC and ALC values will be recorded from the standard of care CBC drawn and their nadirs will be correlated with radiation dose to the pelvic bone marrow.

7.0 STASTICAL PLAN:

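### Section 7.4.1 does not hold the VMAT controls to the section 4 clinical criteria or mask hand-matching to charted toxicity, leaving an avoidable selection-bias risk in the primary grade 3+ comparison, clearest for haematologic toxicity

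*Combined protocol and SAP*

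**What the plan says.** **IMPT patients.** Section 4.1 sets floors for ANC, WBC, platelets and haemoglobin and ceilings for creatinine, bilirubin and AST/ALT. It also requires "Zubrod Performance Status of 0-1 within 60 days prior to registration". On HIV it says "HIV test must be done within 90 days of study registration", and "HIV positive patients are eligible for this study if they have a CD4 count >400 cells/mm3". Section 4.2 lists "other immunocompromised status" among the exclusions.

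**Controls.** Section 7.4.1 defines them as contemporary patients with non-metastatic anal squamous cell carcinoma who received VMAT with 5FU and cisplatin, "manually and individually matched for (in order): T-stage, radiation dose, age and gender". Their data come from records: "A separate PA protocol will be submitted to retrospectively review the data from these contemporary controls". McNemar's test is named for the comparison, without a significance level, sidedness or power.

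**Mitigation offered.** One bullet in section 7.4.1 promises subset analyses of other variables that may affect toxicity. It names none.

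**Reuse.** Secondary Endpoint #7 (costs) and Exploratory Endpoint #2 (blood-count nadirs) refer back to the same controls and add no entry criteria.

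**The concern.** The two groups share diagnosis, absence of metastases and concurrent chemotherapy, and age is handled by matching. They do not share, as written, the criteria closest to haematologic toxicity: baseline counts, performance status, HIV/CD4 and other immune compromise. If some controls would have failed those criteria, they would plausibly have more grade 3+ haematologic events for reasons unrelated to radiation modality. McNemar's test accounts for pairing. It does not correct for differences between pair members on unmatched variables.

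The second gap concerns how pairs are chosen. Matching is by hand from retrospective records, so toxicity may already be visible when one candidate is preferred to another. No age band, tie-break or masking is stated.

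This is the one comparison with VMAT to which section 7.4.1 attaches a formal test, and it is meant to inform a future randomized trial. The same controls feed two further analyses.

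**Working it through.** **The plan's own figures.** The only design calculation given is Table 4, for the BOP2 rule on grade 4+ toxicity in the single arm. Exact binomial recursion over the Table 3 boundaries gives a chance of claiming acceptability of 7.38% at a true rate of 0.5 (stated 7.31%) and 87.50% at 0.3 (stated 87.57%). Expected sample sizes are 26.7 and 39.2 (stated 26.7 and 39.1). Table 4 reproduces and does not involve controls. There is no stated figure to reproduce for the matched comparison.

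**Inputs for the illustration**
- Base grade 3+ haematologic rate 58%: the RTOG 0529 figure in section 7.4.1. Section 3.1 describes that cohort as "patients receiving IMRT with concurrent 5FU and MMC on RTOG 0529 still experienced" toxicity, so the regimen was 5FU/MMC, whereas controls here receive 5FU/cisplatin. It is a reference rate only.
- 40 evaluable patients (section 7.2), taken as 40 pairs.
- Assumed, not in the documents: two-sided 5% test; no within-pair correlation; true IMPT rate 58%; share *s* of controls failing section 4; toxicity rate *q* among them.

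**Shift in the control rate:** 0.58 + s(q − 0.58).
- Low: 0.58 + 0.1 × 0.12 = 0.592 (+1.2 points)
- Mid: 0.58 + 0.2 × 0.22 = 0.624 (+4.4 points)
- High: 0.58 + 0.3 × 0.32 = 0.676 (+9.6 points)

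The 95% CI half-width for the difference is 1.96 × √(2 × 0.58 × 0.42 / 40) = 0.216. The mid-case shift is about one fifth of that (4.4 / 21.6 = 0.20).

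**Chance of a significant result favouring IMPT when true rates are equal** (exact enumeration of the discordant pairs):

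| Control rate | McNemar | Continuity-corrected |
|---|---|---|
| 58.0% (no shift) | 2.6% | 1.3% |
| 59.2% | 3.3% | 1.7% |
| 62.4% | 6.1% | 3.4% |
| 67.6% | 14.3% | 8.8% |

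**The opposite direction.** Let *u* be the share of control events not charted. The shift is cancelled when u = 1 − 0.58 / control rate: 2.0%, 7.1% and 14.2% in the low, mid and high cases. At u = 10% in the mid case the observed control rate is 0.624 × 0.9 = 56.2%. The chance is then 1.8% favouring IMPT and 3.8% favouring VMAT.

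**What restricting eligibility alone would do.** With eligible controls only, the rate at u = 10% is 0.58 × 0.9 = 52.2%, and the chance of a false result favouring VMAT rises from 3.8% to 7.7% (2.0% to 4.4% with continuity correction). In the mid case the net bias without restriction is 0.044 − 0.624u, and with restriction it is −0.58u. The absolute values are equal at u = 0.044 / (0.624 + 0.58) = 3.7%. Above that, restriction alone enlarges net bias. The corresponding thresholds are 1.0% (low) and 7.6% (high).

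**Outcome-aware picking** is not sized. The documents do not say how many candidates would tie on the four variables, and such picking could favour either modality.

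**The case against.** **The separate protocol may cover this.** Control eligibility and abstraction rules would naturally sit there. This stands: what is shown is silence in the text available. A reader might infer that matching will be done with toxicity in view. The documents do not say so; they only omit masking.

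**Subset analyses are planned.** They are, but no variables are named, they cannot undo selection made with outcomes visible, and 40 pairs leave little room. Even the full set has about 44% power for 58% against 38% (33% with continuity correction).

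**The sizes are assumed.** This stands. Section 5.2 lists renal impairment and myelosuppression among cisplatin's effects, so clinicians may already have kept many patients with poor counts or creatinine off this regimen. With 5% ineligible at 80% toxicity, the shift is 0.05 × 0.22 = 1.1 points and the chance favouring IMPT is 3.3%.

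**The consequence is limited.** This also stands. It is a feasibility study and no decision rule hangs on McNemar's test.

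**Hand-matching already follows a fixed order.** Dose depends on tumour size and so overlaps with T-stage, and age narrows the candidates further. That limits discretion by an unknown amount but does not replace a tie-break or masking.

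**Tightening eligibility could worsen net bias.** Correct where control events are under-recorded, as the working shows. This changes the remedy: the laboratory-derived comparison has to be part of it.

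**Conclusion.** The concern holds as an avoidable risk in the text as written, and the remedy is a cheap improvement. Section 7.4.1 sets screened IMPT patients against controls not stated to meet the same clinical criteria, paired by hand without stated masking. Under the assumptions listed, the control rate would rise 1.2-9.6 points and the chance of a false result favouring IMPT would go from 2.6% to 3.3-14.3%.

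A reader might infer that the comparison is biased in favour of IMPT. The documents do not support that. Neither the share of ineligible controls nor their toxicity is given, and modest under-recording (7.1% in the mid case) would cancel or reverse the shift. Nor does the point reach the safety conclusion, since BOP2 uses no controls. Haematologic toxicity is the clearest case; the same gap applies to GI and GU toxicity, which are not sized here.

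**What to change.** In section 7.4.1, and consistently in the separate control-review protocol:

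1. Restrict the control pool to VMAT patients whose pre-treatment charts meet the section 4 clinical criteria that a chart can show: blood counts, creatinine, bilirubin, AST/ALT, performance status, prior malignancy or pelvic radiotherapy, immune status, and CD4 if known HIV positive. Leave out funding, contraception and exact screening windows. As a stated exception, keep controls with no HIV test and no recorded HIV diagnosis, and repeat the analysis without them. Report exclusions separately for failed and for missing items.
2. Match by a fixed algorithm in the order already given, with a pre-set age band and a seeded random tie-break, on a file without toxicity data. Lock the pairs before toxicity is abstracted.
3. Report baseline ANC/WBC, HIV/CD4 and performance status by group.
4. Alongside the charted haematologic comparison, and not as an optional check, compare grade 3+ leukopenia, neutropenia and lymphopenia derived from laboratory nadirs in both groups. Exploratory Endpoint #2 already compares these nadirs. For trial patients section 6.5.2 states: "Blood will be drawn at baseline, weekly during chemoradiation and at the 12-week post-treatment follow up visit as per standard of care". Without this step, step 1 can enlarge net bias against IMPT.

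**Cost.** Some wording, a short matching program, and abstraction of baseline data for candidate controls. The pool shrinks, some age matches loosen, and excluding incomplete charts is itself a selection, hence the reported counts. Count differences above the section 4 floors remain unadjusted. The laboratory-derived comparison covers white-cell toxicity only, with no equivalent for GI or GU events.
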